3. GENERAL ANALYSIS CONSIDERATIONS

3.1. Analysis populations

Full analysis set: All patients that consent to take part in the study within a randomized practice. These participants (practices) will be analysed in the groups to which they were allocated, disregarding protocol deviations or non-compliance. Missing data will be imputed using multiple imputation modelling (see section 3.3). Patients who have not completed the EQ5D-5L because they are deceased will be recorded as having a value of 0.

Complete cases set: All patients that consent to take part in the study within a randomized practice. These participants (practices) will be analysed in the groups to which they were allocated, disregarding protocol deviations or non-compliance. Missing data will not be imputed. Patients who have not completed the EQ5D-5L because they are deceased will be recorded as having a value of 0.

3.2. Derived variables

3.2.1 Primary outcome

A UK value set for the EQ5D-5L is now available⁸, along with a Stata do-file to transform the five EQ5D responses into a single value summarising the respondents' health state.

3.2.2 Secondary outcomes

CARE – 10 item questionnaire (each scored between 1-5), total score is summation of individual scores.⁹

PACIC – 20 item questionnaire (each item scored 1-5), overall score is an average of all 20 items.¹⁰

EQ5D-5L (at 9 months): As calculated for patients in primary outcome.

Bayliss – For each of 27 chronic conditions respondents select those that they experience and rate each selected condition on a five-point scale from 1 (interferes with daily activities "not at all") to 5 (interferes with daily activities "a lot"). Respondents are additionally allowed to add medical conditions not already on the list. The overall score representing level of morbidity is then the sum of conditions selected weighted by the level of interference assigned to each (that is, the sum of the interference scores).¹¹

HADS: Anxiety score – simple addition of the relevant 7 questions; Depression score – simple addition of the relevant 7 questions.¹²

Multimorbidity Treatment Burden Questionnaire – 10 items each scored 0-4. Total score is calculated by calculating the average score for each patient and then multiplying by 2.5 to get a value 0-100.

MMAS – 8 item questionnaire, with 7 questions being binary outcome assigned values 0 or 1, and a single question has values 4, 3, 2, 1 or 0. Questions 1-4 and 6-7 are coded 0 for 'yes' and 1 for 'no'; question 5 is coded 0 for 'no' and 1 for 'yes'. To get total score, add 7 binary questions together, and divide value of other single question by 4, and add them together to get a score between 0-8.¹³

Number of high risk prescribing indicators – This is the number of adverse warnings triggered and can be from 0 upwards.¹⁴

Continuity of care: Visit entropy will be used to measure the continuity of care.

A patient's visit to a healthcare provider can be considered a discrete random variable X. Then X can take on k distinct levels, one for each healthcare provider the patient could visit. It has a probability distribution function p(x) that represents the probability of visiting each healthcare provider.

Visit Entropy H(X) of a discrete random variable X can be calculated as¹⁵:

$$H(\mathbf{X}) = -\sum_{i=1}^{k} p(x_i) \log_2 p(x_i)$$

and the probability of visiting the ith provider is estimated as:

$$\hat{p}(x_i) \approx \frac{n_i + 1/k}{N+1}$$

Where n_i is the number of observed visits to the i^{th} provider, k is the total number of possible providers, and N is the total number of observed visits.

H(X) approaches its minimum value of zero when a patient has perfect continuity of care, visiting only their primary physician, and approaches its maximum when there is no continuity of care.

Visit entropy is a relatively new measure, and is less well recognised than other measures for continuity of care. For this reason, continuity of care index (COCI) will also be considered for comparison.

Continuity of care index (COCI) formula¹⁶:

$$COCI = \frac{(\sum_{j=1}^{M} n_j^2) - N}{N(N-1)}$$

Where N is the total number of visits; n_j is the number of visits to the jth different provider, where j= 1, 2, 3, ... M, and M is the number of potential available providers.

Carers' experience scale – 6 item questionnaire (each item has 3 possible responses). Preference-based index values are available to transform the 6 responses to a profile measure value between 0 and 100^{17} .

EQ5D-5L (carers): As calculated for patients in primary outcome.

Multimorbidity Treatment Burden Questionnaire (carers) – development of final scoring system still under-development.

Quality of disease control – This is based on the Quality and Outcomes Framework (QOF) indicators and uses the 'patient average' method of Reeves *et al*¹⁸. It will be measured as a percentage for each individual patient, where it represents the percentage of QOF chronic disease management indicators that apply to that patient which were successfully met.

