2.10.2. Secondary outcomes

Whilst the primary time point for analyses is 15 months the 3D trial will also consider the potential effectiveness of the 3D intervention at 9 months. Secondary analyses will consider the primary and secondary outcomes at 9 months, rather than employing repeated measures analyses which would estimate the effectiveness of the 3D intervention over the duration of the study and examine if there was a differential effect across time. It is plausible that the 3D intervention will be effective in the short-term only with any effects disappearing by 15 months, this may still warrant its implementation into primary care practice and so its effectiveness at 9 months should be formally tested within this study.

The table below lists the secondary outcomes to be considered in analyses and the time points at which they will be measured (T0=baseline; T1=9 months; T2=15 months). Analyses for each secondary outcome will include adjustment for the relevant measure at baseline (T0).

Table 2: Secondary outcomes to be collected in the 3D study, to be compared between trial arms

Secondary outcome	Source	Scale	Time point		
			т0	T1	T2
Experience of holistic patient-centred care					
CARE measure of relational empathy (GP)	Questionnaire - 10 items	10-50	~	~	1
CARE measure of relational empathy (nurse)	Questionnaire - 10 items	10-50	\checkmark	Х	1
Care related to patients' priorities (LTC6)	Questionnaire – 1 item	1-4	✓	~	1
Care which is joined up (LTC6)	Questionnaire – 1 item	1-4	1	1	~
PACIC measure of chronic disease management	Questionnaire - 20 items	1-5	~	1	1
Overall satisfaction	Questionnaire – 1 item	1-5	1	1	1
Burden of illness measures					
EQ5D-5L	Questionnaire -5 items		✓	~	X
Self-rated health	Questionnaire – 1 item	1-5	\checkmark	\checkmark	1
Bayliss measure of illness burden	Questionnaire – 27+ items	0-145 ²	\checkmark	\checkmark	1
HADS Anxiety score	Questionnaire - 7 items	0-21	\checkmark	✓	1
HADS Depression score	Questionnaire - 7 items	0-21	\checkmark	✓	~
Burden of treatment			1		
Multimorbidity Treatment Burden Questionaire ³	Questionnaire - 10 items	0-100	~	1	1
Medication adherence: MMAS-8	Questionnaire - 8 items	0-8	✓	~	1
Number of drugs prescribed ⁴	Practice records	≥0	\checkmark	X	~
Number of high risk prescribing indicators	Practice records	≥0	\checkmark	X	1
Process measures ⁵					
Continuity of care - COC index	Practice records	0-1	\checkmark	X	1

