6.3. Secondary analyses

All analyses of secondary outcomes will be adjusted for the baseline measure of the outcome (if available) and minimisation variables. Patient level analyses will also adjust for practice (as a random effect). All secondary outcomes will be considered at 9 and 15 months.

The list of variables and planned models of analysis are given in the table below. Distributional checks will be carried out for all outcomes and the most appropriate models selected (for example, for ordinal outcomes mixed-effects ordered logistic models will be performed and assumptions regarding the ordinal nature of responses tested; if not valid alternative multinomial models will be employed). The effect, 95% confidence interval and P value will be reported for each model along with the ICC if possible.

Table 6: Planned analyses - Patient level secondary outcomes

Outcomes	Type of variable	Type of model ¹
CARE measure of relational empathy (GP)	Continuous	Mixed-effects linear regression
CARE measure of relational empathy (nurse)	Continuous	Mixed-effects linear regression
Care related to patients' priorities (LTC6)	Discrete (ordinal)	Mixed-effects ordered logistic regression
Care which is joined up (LTC6)	Discrete (ordinal)	Mixed-effects ordered logistic regression
PACIC measure of chronic disease management	Continuous	Mixed-effects linear regression
Overall satisfaction	Discrete (ordinal)	Mixed-effects ordered logistic regression
EQ5D-5L	Continuous	Mixed-effects linear regression
Self-rated health	Discrete (ordinal)	Mixed-effects ordered logistic regression
Bayliss measure of illness burden	Continuous	Mixed-effects linear regression
HADS Anxiety score	Continuous	Mixed-effects linear regression
HADS Depression score	Continuous	Mixed-effects linear regression
Multimorbidity Treatment Burden Questionnaire	Continuous	Mixed-effects linear regression
Medication adherence: MMAS-8	Continuous	Mixed-effects linear regression
Number of drugs prescribed	Count data	Poisson regression random effects
Number of high risk prescribing indicators	Count data	Poisson regression random effects
Continuity of care - COC index	Continuous	Mixed-effects linear regression
Continuity of care - Visit Entropy	Continuous	Mixed-effects linear regression
Quality of disease management	Continuous	Mixed-effects linear regression
Number of hospital admissions	Count data	Poisson regression random effects
Number of outpatient attendances	Count data	Poisson regression random effects

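### The scoring rule for the patient Multimorbidity Treatment Burden Questionnaire (average × 2.5) gives 0–10, not the stated 0–100

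*SAP*

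**What the plan says.** SAP section 3.2.2 describes the patient instrument as "Multimorbidity Treatment Burden Questionnaire – 10 items each scored 0-4" and gives the derivation in the next sentence: "Total score is calculated by calculating the average score for each patient and then multiplying by 2.5 to get a value 0-100". Table 2 in section 2.10.2 lists the instrument under burden of treatment as "Questionnaire - 10 items 0-100", collected at baseline, 9 months and 15 months. A footnote to that table says the questionnaire was developed for this trial.

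Table 6 in section 6.3 plans the analysis as "Multimorbidity Treatment Burden Questionnaire Continuous Mixed-effects linear regression". Section 6.3 adds adjustment for the baseline measure and asks for the effect, its 95% confidence interval and P-value, and the ICC where possible.

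The carer version is separate. Section 3.2.2 says of it: "Multimorbidity Treatment Burden Questionnaire (carers) – development of final scoring system still under-development".

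Nowhere does the SAP give another multiplier for the patient score or define the average differently.

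**The concern.** The multiplier and the range in one sentence cannot both be right. This is an operative derivation for an outcome that will be compared between arms, and treatment burden is named in objective 2 (section 2.1.2).

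Section 1 says the plan should let someone else carry out the analysis if the usual analyst is absent. For this instrument section 3.2.2 is the only scoring source in the document. CARE, PACIC, Bayliss, HADS and MMAS-8 each carry a literature reference there, and this questionnaire carries none. An analyst who doubted the line would find nothing in the SAP to settle it.

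What is at stake is the unit of the reported results. A reader told that the scale runs from 0 to 100, but shown estimates on a 0–10 scale, would take any difference to be ten times smaller than it is.

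**Working it through.** **Inputs.** Number of items: 10 (section 3.2.2 and Table 2). Item range: 0 to 4 (section 3.2.2). Multiplier: 2.5, applied to the patient's average (section 3.2.2). Declared range: 0–100 (section 3.2.2 and Table 2).

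**Attempt to reproduce the declared range.** The extremes are all items at 0 and all items at 4.

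| Rule | All items 0 | All items 4 |
|---|---|---|
| Average × 2.5 (as written) | 0 × 2.5 = 0 | 4 × 2.5 = 10 |
| Sum × 2.5 | 0 × 2.5 = 0 | (10 × 4) × 2.5 = 100 |
| Average × 25 | 0 × 25 = 0 | 4 × 25 = 100 |

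The written rule does not reproduce 0–100. The multiplier needed on the average is 100 / 4 = 25; the multiplier needed on the 10-item sum is 100 / 40 = 2.5. For average × 2.5 to reach 100, items would have to run up to 100 / 2.5 = 40, against the stated 0–4. The written rule is therefore low by a factor of 25 / 2.5 = 10.

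**Effect on the planned analysis.** Let Y be the score on 0–100 and Y* = Y / 10 the score under the written rule, with the baseline score divided by 10 as well. In a mixed-effects linear regression of Y* on arm, baseline Y* and the minimisation variables:

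- the arm coefficient, its standard error and its confidence limits are each divided by 10;
- the test statistic is (b / 10) / (SE / 10) = b / SE, so the P-value is unchanged;
- the between-practice and residual variances are both divided by 100, so the ICC, which is the between-practice variance over their total, is unchanged;
- a standardised effect is (b / 10) / (SD / 10) = b / SD, also unchanged.

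A check on artificial data (200 respondents per arm, simple two-sample t-test, no clustering) shows the same. The difference was −1.0875 with × 2.5 and −10.875 with × 25, with t = −9.385 and the same P-value both times. These figures only illustrate the rescaling; they say nothing about the trial's likely effect.

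**Whether the two repairs agree.** With all 10 items answered, average × 25 = (sum / 10) × 25 = sum × 2.5, so they are identical. With an item missing they need not be. Suppose nine items are scored 2 and one is blank:

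- average of the nine answered items × 25 = 2 × 25 = 50;
- sum × 2.5 with the blank counted as zero = 18 × 2.5 = 45;
- if all 10 items are required, there is no score.

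So the corrected text must not leave the treatment of missing items open.

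**The case against.** The strongest reply is that this is a slip that gives itself away. The target range is stated twice, and both natural repairs agree for complete questionnaires, so the intended scale is not in doubt. The SAP plans summaries by arm (section 6.1) and distributional checks (section 6.3), and a score that never exceeded 10 would probably be noticed there. Even if it were not, no hypothesis test would change. Most of this stands: it limits the consequence and makes it conditional on literal coding. It does not make the sentence correct, and a scoring rule should not depend on the analyst noticing that it fails.

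A reader might infer more than the document supports, in three ways.

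- *That all treatment-burden results are affected.* They are not. Table 2 also lists MMAS-8, number of drugs prescribed and high risk prescribing indicators under burden of treatment, and none uses this rule. The carer version has no scoring rule yet, so the rule does not reach it.
- *That conclusions about benefit could change.* A constant rescaling in both arms and at all time points leaves P-values, the ICC, standardised effects and the direction of effect as they were.
- *That the repair should be the mean of whichever items were answered.* That adds a missing-item rule. Section 3.3 confines secondary outcomes to complete cases unless a validated questionnaire's own guidelines allow a score with items missing, and the SAP cites no such guideline for this instrument.

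**Conclusion.** The rule is wrong as written. It yields 0–10 and contradicts the 0–100 range in the same sentence and in Table 2. If it is programmed literally, the means, standard deviations, adjusted differences and confidence limits of this one patient-reported secondary outcome would be exactly one tenth of the declared scale. A 5-point difference on 0–100, taken purely as an illustration, would appear as 0.5.

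The size of the error follows from the item range and multiplier alone. That any reported result would be affected assumes literal coding. The scoring code is not part of the document, so nothing here shows that it contains the error. The primary EQ5D-5L analysis and the sample size do not use this score.

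**What to change.** In section 3.2.2, replace the rule with: *total score = average of the 10 items × 25 (equivalently, sum of the 10 items × 2.5), range 0–100.* State that missing items are handled under section 3.3: complete case, unless a scoring guideline for this questionnaire allows otherwise, in which case cite it and give its limit on missing items. Table 2 needs no change. Then check that the scoring code matches the corrected line, for example by confirming that a respondent with every item at 4 scores 100. The cost is one line of SAP text, an entry in the amendment table in section 8 and, if the code follows the present wording, one line of code.

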3.3. Procedures for missing data

Missing data may arise as some participants may not return their questionnaires. It is anticipated that proportions with missing data will be similar between the two randomization arms but this will be examined and reported. Baseline characteristics will be compared between participants with and without 15-month follow-up data. In all tables missing data will be indicated by footnotes.

The primary analysis for EQ5D-5L (section 6.2) will include the full analysis set (section 3.1), including all patients in the groups to which they were allocated and imputing missing data. Reasons for missingness will be explored. Missing data will be imputed using multiple imputation techniques such as multiple imputation by chained equations (MICE). Imputation models will include baseline, 9 month and 15 month EQ5D-5L data (as available), intervention arm, stratifying/minimisation variables, as well as other variables such as baseline covariates and auxiliary covariates that are informative of missingness. To allow for clustering in Stata, imputations will be used for the primary analysis and the economic evaluation if possible. The influence of missing data on the primary analysis will be investigated in sensitivity analyses using complete case data only (section 6.5).

The analyses of secondary outcomes will use complete case data only. The only exception to this is for secondary outcomes derived from several items within a validated questionnaire, where questionnaire guidelines specifically state that an overall score can be derived even in the presence of missing data for one (or more) item(s). For example, for HADS anxiety and depression scores, questionnaire guidelines state that the score for a single missing item from a subscale is inferred by using the mean of the remaining six items; however, if more than one item is missing from that subscale the overall score is missing (and the observation excluded from the analysis). The numbers (percentage) of missing data will be presented in tables of secondary outcomes.

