2.6. Randomisation procedures

To minimise post-randomisation selection bias, practices will not be randomised until after patients have been identified and after the initial patient invitations have been mailed.

Practices will be randomised using an algorithm written in advance by the Bristol Randomised Trials Collaboration (BRTC, UKCRC registration ID: 2) on a 1:1 ratio to receive either the intervention or continue care as usual (control group). Randomisation will be stratified by recruiting centre (Bristol, Manchester, and Glasgow) and minimised by practice deprivation level and practice size. Practices within each area will be randomized using a block size of two (one randomized to the 3D intervention and the other to usual care), to ensure balance across the treatment arms given the relatively small number of practices. Within each centre, each block of two practices will be randomized at the same time in the following way.

Within each centre, the initial block of two will be randomized using simple randomization, such that one is allocated to intervention and the other control. For each subsequent block of practices, an algorithm (written within Stata specifically for this study) will determine the allocation of the two practices which creates the best balance in terms of size and deprivation and then weights the randomisation in favour of this allocation (rather than being deterministic); the weights being determined by the degree of imbalance in terms of size and deprivation (see Table 1 and example below).

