6.2. Primary analysis

The tested null hypothesis is that the mean quality of life (measured by the EQ5D-5L) for patients receiving the 3D intervention is the same as for those receiving usual care at 15 months follow up.

Primary analysis will take the form of mixed-effects multivariable linear regression, adjusted for practice (random effect to account for clustering), minimisation variables (practice size and practice deprivation score) and patient baseline EQ5D-5L. The results will be presented as the difference between group means, corresponding 95% confidence interval and P-value. The intra-class correlation (ICC) will also be reported, with a 95% confidence interval. Practices/patients will be analysed in the groups to which they were allocated and missing data will be imputed (section 3.3).

The distribution of EQ5D-5L and model residuals will be examined (a suitable transformation or a boot-strapped 95% confidence interval accounting for clustering²¹ will be considered if necessary).

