6.6. Potential effect modifiers

Potential effect modifiers, selected *a priori* and informed by previous evidence, will be explored using appropriate interaction terms added to the regression models used for the primary analysis. Subgroup analyses of the primary outcome will explore differences in the effectiveness of the 3D intervention compared to usual care according to baseline measures of:

- Participant age (< median / ≥ median of consenting participants);
- Number of long term conditions as defined in section 2.4.3 (< median / ≥ median of consenting participants);
- Deprivation (quartiles of consenting participants);
- Depression alongside physical health problems (presence/absence).

Subgroup analyses are likely to be insufficiently powered since the trial was not powered to specifically test these effects. These subgroup analyses will therefore be hypothesis generating and will focus on interpretation of 95% confidence intervals rather than P-values.

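### Section 3.3 names no practice term and no clustering method for the imputation; if run single-level as listed, the primary SE is about 4–9% too small, and section 6.6 interactions are shrunk

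*SAP*

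**What the plan says.** Section 3.3 puts imputed data into the primary analysis and gives chained equations as an example of the technique. On content it says "Imputation models will include baseline, 9 month and 15 month EQ5D-5L data (as available), intervention arm, stratifying/minimisation variables", and continues "as well as other variables such as baseline covariates and auxiliary covariates that are informative of missingness". The stratifying and minimisation variables come from section 2.6: "Randomisation will be stratified by recruiting centre (Bristol, Manchester, and Glasgow) and minimised by practice deprivation level and practice size". All three describe the practice, but none identifies it.

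The only mention of clustering in the imputation is "To allow for clustering in Stata, imputations will be used for the primary analysis and the economic evaluation if possible". This says where imputations will be used, and that only if possible. It does not say how practice enters them.

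The analysis model in section 6.2 is "adjusted for practice (random effect to account for clustering), minimisation variables (practice size and practice deprivation score) and patient baseline EQ5D-5L", and section 6.2 also promises the ICC with a 95% confidence interval. In section 6.6 the effect modifiers "will be explored using appropriate interaction terms added to the regression models used for the primary analysis", that is, to models fitted to imputed data. Section 3.3 does not say whether imputation is done by arm or with arm-by-subgroup terms.

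**The concern.** An imputation model should carry at least the structure of the analysis model it feeds. If practice is left out, each missing value is drawn as if the patient were independent of others in the same practice, beyond what the covariates explain. The completed data then contain too little between-practice variance, the mixed model estimates too small a practice effect, and the primary confidence interval is too narrow. The error is anti-conservative, and it also carries into the ICC that the plan will report.

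The same reasoning applies to effect modification. If imputed values carry no arm-by-subgroup difference, an interaction fitted afterwards is diluted by the imputed patients.

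Section 1 of the SAP sets itself the aim of letting another statistician carry out the analysis. Two analysts could follow section 3.3 in good faith, one with single-level and one with multilevel imputation, and report different primary intervals.

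**Working it through.** **Inputs.** From SAP section 2.7: 32 practices (16 per arm), 1382 participants, 80% followed up, ICC 0.03, effect size 0.274 SD, 5% significance (taken as two-sided). The 80% is quoted there for 12 months; I use it as the observed fraction p for the 15-month outcome.

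**The plan's own figure.** Analysed patients per practice are 1382 × 0.8 / 32 = 34.55. The design effect is 1 + (34.55 − 1) × 0.03 = 2.007, and the effective size per arm is (1382 × 0.8 / 2) / 2.007 = 275.5. Power = Φ(0.274 / √(2/275.5) − 1.96) = 89.5%, which reproduces the stated figure of around 90%.

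**Analytic check of single-level imputation.** Take unit outcome variance, m = 1382/32 = 43.19 patients per practice, p = 0.8, ρ = 0.03, many imputations, and a practice effect not explained by the covariates.

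- Two patients in a practice share the practice effect only if both are observed, so the completed-data ICC is ρ′ = p²ρ = 0.64 × 0.03 = 0.0192.
- Within-imputation variance of the arm difference: W = (2/16) × [ρ′ + (1 − ρ′)/m] = 0.125 × (0.0192 + 0.9808/43.19) = 0.00524.
- Between-imputation variance: B = 2(1 − p)/(p × 16 × m) = 0.4/(0.8 × 691) = 0.00072.
- Variance reported by Rubin's rules: W + B = 0.00596.
- True variance: (2/16) × [ρ + (1 − ρ)/(mp)] = 0.125 × (0.03 + 0.97/34.55) = 0.00726.
- SE ratio: √(0.00596/0.00726) = 0.906. The type I error is 2 × [1 − Φ(1.96 × 0.906)] = 7.6%.

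A separate analytic calculation gave 0.905 and 7.6% for this case. Over other inputs it ran from 0.97 (ICC 0.01, 10% missing; 5.6%) to 0.84 (ICC 0.05, 30% missing; 10.2%).

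**Simulation with the planned type of model.** 500 trials, 32 practices of 43, ICC 0.03 after baseline adjustment, 20% missing completely at random, 20 imputations, random-intercept REML, true interaction 0.20 SD with a binary subgroup. The subgroup's main effect was in every imputation model. The 9-month score, where used, was complete, with an assumed residual correlation of 0.7 with the 15-month score.

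| Imputation | Mean reported SE | Estimated ICC | Interaction |
|---|---|---|---|
| Single-level | 0.0769 | 0.019 | 0.161 |
| Multilevel | 0.0847 | 0.029 | 0.162 |
| Single-level, with 9-month score | 0.0784 | 0.024 | 0.184 |
| Multilevel, with 9-month score | 0.0815 | 0.028 | 0.184 |
| Multilevel, with arm-by-subgroup term | 0.0847 | 0.029 | 0.203 |

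- SE shortfall without the 9-month score: 1 − 0.0769/0.0847 = 9%.
- SE shortfall with it: 1 − 0.0784/0.0815 = 4%. At a ratio of 0.96 the type I error is 2 × [1 − Φ(1.96 × 0.96)] = 6.0%.
- Interaction shrinkage: (0.20 − 0.162)/0.20 = 19% without the 9-month score, close to the missing fraction, and (0.20 − 0.184)/0.20 = 8% with it.
- The practice term does not repair the interaction (0.162). The arm-by-subgroup term does (0.203).

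The simulated rejection rates on a t(30) reference were 8.4% for single-level and 6.4% for multilevel imputation without the 9-month score. With 500 trials these are uncertain by about √(0.05 × 0.95/500) = 1 percentage point, and the empirical SE by about 3%. The size therefore rests on the mean reported SEs and the analytic ratio.

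A second simulation (3000 null trials, imputing from arm and baseline only, practice-mean analysis) gave an SE 8% too small and 6.6% type I error at 20% missing. Complete-case analysis of the same data gave about 5%.

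**The case against.** A reader might infer that the plan excludes practice from the imputation, so that the primary SE is certain to be too small. The text does not support that. The covariate list is open-ended, chained equations are only an example, and the clustering sentence, though it reads as incomplete, shows that clustering was meant to be handled. The defect is that no method is fixed and the variables actually named omit practice.

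A reader might also infer that arm enters only as a main effect and that this harms the primary result. The plan says only that arm is included, and a main effect is adequate for the primary comparison. Only the interactions suffer, and section 6.6 itself calls those analyses hypothesis generating and likely underpowered.

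On size, several points stand:

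- The plan names 9-month EQ5D-5L, which brings the shortfall down to about 4% if complete. Some patients missing at 15 months will also lack the 9-month score, so 4–9% is the fair range.
- Centre, size and deprivation may explain some practice variation and reduce the shortfall further.
- Deaths are scored 0 (section 3.1), so the imputed share is below 20% if that loss includes deaths.
- The design effect of about 2 is not what is lost, since the analysis model keeps its practice random effect.
- A complete-case sensitivity analysis is planned (section 6.5.2) and would be a fair comparator under the simulated conditions.

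The last point does not remove the problem. The primary interval comes from the imputed data, and a wider complete-case interval could be read as lost information when the imputed one is simply too narrow.

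**Conclusion.** The point holds in conditional form and concerns the primary analysis. Followed literally and single-level, section 3.3 feeds the mixed model from an imputation that ignores the model's own random effect. The practice term is the part that matters. The interaction point is a lesser, separate one that needs its own remedy.

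The sizes in the working assume data missing completely at random, equal practice sizes, ICC 0.03 remaining after covariate adjustment, and 20% of 15-month values imputed. The lower end of each range assumes a complete 9-month score with the correlation stated there.

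**What to change.** Replace the clustering sentence in section 3.3 with wording such as:

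> Imputation will allow for clustering by including practice as a random intercept (multilevel imputation) or, if that is not feasible, as practice indicators within arm, in which case centre, size and deprivation are dropped from the imputation model as collinear. Imputation will be done separately by arm, with the section 6.6 subgroup variables in the model.

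The first sentence deals with the standard error and the ICC, the second with the interactions. No new data are needed. The cost is slightly longer code, possibly an add-on package for multilevel imputation, and mildly conservative standard errors if practice indicators are used at a low ICC.
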